**PROTOCOL SYNOPSIS (CONTINUED)**

Study Population (Continued)	Exclusion Criteria
	
 
1. Clinically significant abnormalities in medical history (e.g., previous acute coronary syndrome within 6 months of screening, major surgery within 3 months of screening, type I diabetes mellitus) or physical examination
 
2. History of secondary HTN
 
3. Subject with borderline orthostatic hypotension (assessed at Screening), when they assume a standing position (within 3 minutes of standing up), defined as: 
 
a. A decrease in SBP of <math>\geq 17</math> mmHg or
 
b. A decrease in DBP of <math>\geq 7</math> mmHg
 
 
 
4. The use of the following at time of screening and during the course of the study: 
 
a. Other medications for the treatment of HTN (e.g., clonidine, guanfacine, guanabenz, alpha-methyldopa, hydralazine, minoxidil, diazoxide, renin inhibitors)
 
b. Medications that may cause hyperkalemia (e.g., cyclosporine or tacrolimus, pentamidine, trimethoprim-sulfamethoxazole, all heparins)
 
c. Oral or subcutaneous (SC) anticoagulants (e.g., warfarin, rivaroxaban, apixaban, heparin, lovenox)
 
d. Organic nitrate preparations (e.g., nitroglycerin, isosorbide mononitrate, isosorbide dinitrate, or pentaerythritol)
 
e. Phosphodiesterase 5 inhibitors (e.g., sildenafil, tadalafil, vardenafil, avanafil)
 
f. Potassium sparing diuretics (e.g. eplerenone, spironolactone, amiloride, triamterene)
 
 
 
5. Treatment with another Study Drug, biological agent, or device within 1 month of screening, or 5 half-lives of study agent, whichever is longer
 
6. Previous treatment with an oligonucleotide or other RNA therapeutic (including siRNA) within 4 months of screening if single dose received, or within 12 months of screening if multiple doses received
 
7. Active infection with HIV, hepatitis C or hepatitis B diagnosed by initial serological testing and confirmed with RNA testing, or prior treatment for hepatitis C. Patients at Screening who test positive by serology, but negative by RNA may be allowed in consultation with the Sponsor Medical Monitor
 
8. Malignancy within 5 years, except for basal or squamous cell carcinoma of the skin or carcinoma in situ of the cervix that has been successfully treated. Subjects with a history of other malignancies that have been treated with curative intent and which have no recurrence within 5 years may also be eligible if reviewed by the Sponsor Medical Monitor
 
9. History of bleeding diathesis, coagulopathy, immune thrombocytopenic purpura, thrombotic cytopenic purpura, or any qualitative or quantitative platelet defect
 

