## 5.2. Exclusion Criteria

1. Clinically significant abnormalities in medical history (e.g., previous acute coronary syndrome within 6 months of screening, major surgery within 3 months of screening, type I diabetes mellitus) or physical examination
2. History of secondary HTN
3. Subject with borderline orthostatic hypotension (assessed at Screening), when they assume a standing position (within 3 minutes of standing up), defined as:
  - a. A decrease in SBP of  $\geq 17$  mmHg or
  - b. A decrease in DBP of  $\geq 7$  mmHg
4. The use of the following at time of screening and during the course of the study:
  - a. Other medications for the treatment of HTN (e.g., clonidine, guanfacine, guanabenz, alpha-methyldopa, hydralazine, minoxidil, diazoxide, renin inhibitors)
  - b. Medications that may cause hyperkalemia (e.g., cyclosporine or tacrolimus, pentamidine, trimethoprim-sulfamethoxazole, all heparins)
  - c. Oral or SC anticoagulants (e.g., warfarin, rivaroxaban, apixaban, heparin, lovenox)
  - d. Organic nitrate preparations (e.g., nitroglycerin, isosorbide mononitrate, isosorbide dinitrate, or pentaerythritol)
  - e. Phosphodiesterase 5 inhibitors (e.g., sildenafil, tadalafil, vardenafil, avanafil)
  - f. Potassium sparing diuretics (e.g., eplerenone, spironolactone, amiloride, triamterene)
5. Treatment with another Study Drug, biological agent, or device within 1 month of screening, or 5 half-lives of study agent, whichever is longer
6. Previous treatment with an oligonucleotide or other RNA therapeutic (including siRNA) within 4 months of screening if single dose received, or within 12 months of screening if multiple doses received
7. Active infection with human immunodeficiency virus (HIV), hepatitis C (HCV) or hepatitis B (HBV) diagnosed by initial serological testing and confirmed with RNA testing, or prior treatment for hepatitis C. Patients at Screening who test positive by serology, but negative by RNA may be allowed in consultation with the Sponsor Medical Monitor
8. Malignancy within 5 years, except for basal or squamous cell carcinoma of the skin or carcinoma *in situ* of the cervix that has been successfully treated. Subjects with a history of other malignancies that have been treated with curative intent and which have no recurrence within 5 years may also be eligible if reviewed by the Sponsor Medical Monitor

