#### 6.1.1. Screening

Written informed consent for the study will be obtained prior to the performance of any study-related procedures including screening procedures. A 4-week period is provided for completing screening assessments and determining subject eligibility for the study. Safety labs may be re-tested up to 2 additional times for determination of subject eligibility after consultation with the Sponsor Medical Monitor. AGT may be re-tested up to 1 additional time for determination of subject eligibility after consultation with the Sponsor Medical Monitor.

During the Screening Period, subjects will undergo a medical history (including cardiovascular disease risk factors) and physical examination including vital signs, orthostatic hypotension assessment, 12-lead ECG, and have blood and urine samples taken for clinical laboratory testing. Subjects will be screened for HIV, HepB, and HCV.

During the Screening Period the study site will also education subjects regarding a low sodium diet.

The study site will record basic personal details about you, including your name, contact details, gender, height, weight, date of birth, age, ethnicity, and racial origin (to be used only for clinical purposes), as well as information on your medical history, and clinical data collected about your participation in the study.

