#### 8.5.1. Safety Monitoring Rules for Liver Chemistry Tests

The following rules are adapted from the draft guidance for industry, “Drug-Induced Liver Injury: Premarketing Clinical Evaluation,” issued by the U.S. Department of Health and Human Services, Food and Drug Administration, July 2009.

In the event of an ALT or AST measurement that is  $> 3 \times$  ULN at any time during the Study (Treatment or Post-Treatment Period), the initial measurement(s) should be confirmed as described above ideally within 48 to 72 hours. Liver chemistry tests (ALT, AST, ALP, INR, and total bilirubin) should be tested ideally within 48 to 72 hours as well. Additional, confirmatory measurements should also be performed if ALT or AST levels increase to  $5 \times$  ULN.

Frequency of Repeat Measurements: Subjects with confirmed ALT or AST levels  $> 3 \times$  ULN should have their liver chemistry tests (ALT, AST, ALP, international normalized ratio (INR) and total bilirubin) retested 2 to 3 times weekly. The frequency of retesting may decrease to once a week or less until ALT or AST levels become  $\leq 1.2 \times$  ULN or return to baseline levels or Study Drug has been discontinued and the subject is asymptomatic.

Further Investigation into Liver Chemistry Elevations: For subjects with confirmed ALT or AST levels  $> 3 \times$  ULN, the following evaluations should be performed:

1. Obtain a more detailed history of symptoms and prior and concurrent diseases
2. Obtain further history for concomitant drug use (including nonprescription medications, herbal and dietary supplement preparations), alcohol use, recreational drug use, and special diets
3. Obtain a history for exposure to environmental chemical agents and travel
4. Serology for viral hepatitis (HAV IgM, HBsAg, HCV antibody, Cytomegalovirus (CMV), immunoglobulin M (IgM), and Epstein-Barr Virus antibody panel)
5. Serology for autoimmune hepatitis (e.g., antinuclear antibody [ANA])
6. Additional tests may be conducted to rule out:
  - Nonalcoholic steatohepatitis
  - Hypoxic/ischemic hepatopathy
  - Biliary tract disease
  - Hepatitis types D and E

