#### **8.6.1. Stopping Rules for Liver Chemistry Elevations**

In the event of laboratory results meeting the following criteria, **and the event is without an alternative explanation as discussed with the Sponsor Medical Monitor**, dosing of a subject with Study Drug (ISIS 757456 or placebo) will be stopped permanently; values that are not confirmed due failure to retest or missing lab values will be presumed confirmed:

1. ALT or AST  $> 8$  x ULN, which is confirmed
2. ALT or AST  $> 5$  x ULN, which is confirmed and persists for  $\geq 2$  weeks
3. ALT or AST  $> 3$  x ULN, which is confirmed **and** total bilirubin  $> 2$  x ULN or INR  $> 1.5$

4. ALT or AST > 3 x ULN which is confirmed, **and** the new appearance (i.e., onset coincides with the changes in hepatic enzymes) of fatigue, nausea, vomiting, right upper quadrant pain or tenderness, fever, rash, and/or concomitant eosinophilia (> ULN)

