## **APPENDIX B. LIST OF LABORATORY ANALYTES**

**Appendix B List of Laboratory Analytes**

Based on emerging data from this or future studies, additional tests not listed below may be performed on stored samples to better characterize the profile of ISIS 757456 or other similar oligonucleotides.

Clinical Chemistry Panel
 
 
• Sodium
 
• Potassium
 
• Chloride
 
• Bicarbonate
 
• Total protein
 
• Albumin
 
• Calcium
 
• Magnesium
 
• Phosphorus
 
• Glucose
 
• BUN
 
• Creatinine
 
• Creatinine Clearance
 
• Uric Acid
 
• Total bilirubin
 
• Direct (conjugated) bilirubin
 
• Indirect (unconjugated) bilirubin
 
• ALT
 
• AST
 
• Alkaline phosphatase
 
• Creatinine kinase
 
• GGT
 
 
Thyroid Panel
 
 
• TSH
 
• Free T4
 
• Free T3
 
	
Screening Tests
 
 
• Hepatitis B surface antigen
 
• Hepatitis C antibody
 
• HIV antibody
 
• FSH (women only, if applicable)
 
• Serum beta-subunit of human chorionic gonadotropin (βhCG) (women only, if applicable)
 
 
Coagulation
 
 
• aPTT (sec)
 
• PT (sec)
 
• INR
 
 
Efficacy
 
 
• Plasma AGT
 
 
Pharmacokinetics
 
 
• ISIS 757456 levels in plasma
 
 
Immunogenicity
 
 
• Anti-ISIS 757456 antibodies
 
 
Renal Urine Biomarkers
 
 
• NGAL
 
• NAG
 
• KIM-1
 
	
Hematology
 
 
• Red blood cells
 
• Hemoglobin
 
• Hematocrit
 
• MCV, MCH, MCHC
 
• Platelets
 
• White blood cells
 
• WBC Differential (% and absolute)
 
• Neutrophils
 
• Eosinophils
 
• Basophils
 
• Lymphocytes
 
• Monocytes
 
 
Exploratory
 
 
• Angiotensin II
 
• Renin (PRA)
 
• Renin (ARC)
 
• Plasma Aldosterone
 
• Angiotensin I
 
• Angiotensin (1-7)
 
• Angiotensin III
 
• Angiotensin IV
 
• B-type natriuretic peptide
 
• Atrial natriuretic peptide
 
• Plasma Nephilysin
 
• Endothelin I
 
	
Inflammatory
 
 
• Hs-CRP
 
 
Urinalysis
 
 
• Color
 
• Appearance
 
• Specific gravity
 
• pH
 
• P/C Ratio (UPCR)
 
• Protein
 
• Blood
 
• Ketones
 
• Urobilinogen
 
• Glucose
 
• Bilirubin
 
• Leukocyte esterase
 
• Nitrate
 
• Microscopic examination
 
• Angiotensinogen
 
• Albumin
 
• Creatinine
 
• Protein
 
• Sodium^3
 
• Cortisol
 
• Aldosterone
 
• A/C Ratio (UACR)
 

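### Exclusion 7 confirms hepatitis B, a DNA virus, by RNA testing, so an RNA result is the wrong basis for considering a surface-antigen-positive subject for entry

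*Combined protocol and SAP*

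**What the plan says.** Protocol 5.2, item 7 excludes active infection with HIV, hepatitis C or "hepatitis B (HBV) diagnosed by initial serological testing and confirmed with RNA testing, or prior treatment for hepatitis C". The synopsis carries the same rule: "hepatitis C or hepatitis B diagnosed by initial serological testing and confirmed with RNA testing". The sentence that follows opens a discretionary route for all three viruses without distinction: "Patients at Screening who test positive by serology, but negative by RNA may be allowed in consultation with the Sponsor Medical Monitor".

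Section 6.1.1 says only this about viral testing: "Subjects will be screened for HIV, HepB, and HCV". Appendix A schedules these tests at Screening alone. Under Screening Tests, Appendix B lists an antibody test for hepatitis C, an antibody test for HIV and, for hepatitis B, one marker: "Hepatitis B surface antigen". Exclusion 7, Appendix A and Appendix B name no hepatitis B DNA test.

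Section 2.2 places the more prominent effect of GalNAc-conjugated oligonucleotides in the liver.

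**The concern.** A rule of serology first and RNA second works where the first test is an antibody and the virus carries RNA. A hepatitis C antibody can outlast the infection, and an RNA test can settle whether virus is present. HIV is likewise screened by antibody and confirmed by RNA.

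Hepatitis B fits neither half of that rule. Its genome is DNA, so the routine test for circulating virus is a DNA test. Its screening test here is an antigen, which points to current infection rather than past exposure. Read as written, the criterion uses an RNA result to decide whether an antigen-positive subject counts as actively infected and, if not, whether that subject may be considered for entry. At stake is the eligibility of a few subjects with possible current hepatitis B in a trial of a liver-directed drug, and whether the consultation is informed by a result that answers the right question.

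**Working it through.** The plan gives no figure on this point, so the check is mainly a reading of the passages side by side. Two facts are general knowledge and not in the documents: hepatitis B is a DNA virus, and surface antigen marks current infection.

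**Step 1: what counts as positive serology for hepatitis B.** Appendix B lists surface antigen as the only hepatitis B screening marker. For this virus, positive by serology can therefore only mean surface-antigen positive.

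**Step 2: apply Exclusion 7 literally to a surface-antigen-positive subject.**
- RNA positive: confirmed, so excluded.
- RNA negative: not confirmed, so not excluded by the first sentence. The second sentence lets the subject be considered with the Medical Monitor.
- No RNA test run, because it is not the routine test for this virus: not confirmed, but not RNA-negative either. Neither sentence applies.

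**Step 3: do other exclusions catch such a subject?**
- Exclusion 12 covers active infection needing systemic therapy that will not be finished before Day 1. It misses an untreated carrier.
- Exclusion 14c covers liver tests above 1.5 x ULN. It misses a carrier at or below that limit.
- The opening words of exclusion 14 (other clinically significant screening laboratory abnormalities) and exclusion 18 (Investigator or Sponsor opinion) could cover the case, but both depend on judgement.

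No exclusion bars surface-antigen positivity as such.

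**Step 4: would replacing RNA by DNA be enough?** Suppose the first sentence names DNA for hepatitis B and the second sentence is limited to the RNA viruses. An antigen-positive, DNA-negative subject is then not a confirmed infection, and is no longer covered by the only sentence in item 7 that requires consultation. That subject falls outside both sentences. The test name and the handling of a positive antigen must be settled together.

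**Step 5: size.** The documents give no prevalence. Assume 0.3% to 1% surface-antigen positive. Also assume that carriers pass every other gate as often as anyone else, all test RNA-negative, and the Medical Monitor agrees every time. The right denominator is the approximately 30 subjects randomised, not everyone screened.
- Expected number: 30 x 0.003 = 0.09; 30 x 0.01 = 0.30.
- Chance of at least one: 1 - 0.997^30 = 8.6%; 1 - 0.99^30 = 26%.

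For the assumed prevalence range these are ceilings, because each gate in Step 3 and the consultation itself can only lower them.

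**The case against.** The strongest reply is that the wording is a slip for nucleic acid testing in general, that nobody enters without sponsor involvement, and that the exclusions in Step 3 add further checks. Much of this stands. Entry is never automatic, and a Medical Monitor told of a positive surface antigen may well decline. But the text gives no wider meaning to RNA and repeats the word in the synopsis. The discretionary decision would also still rest on a result that does not bear on hepatitis B.

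A reader might go further and infer that an admitted carrier would undermine the liver safety comparison. The argument would be that the liver stopping rules in 8.6.1 apply only when they are met "and the event is without an alternative explanation as discussed with the Sponsor Medical Monitor", and that the work-up in 8.5.1 includes "Serology for viral hepatitis (HAV IgM, HBsAg, HCV antibody", so the carrier would bring a ready explanation for any ALT rise. The documents do not support that conclusion:
- SAP 3.7.3 tabulates confirmed ALT/AST above 3 x ULN and above 5 x ULN by treatment group with no filter on attribution. An alternative explanation removes nobody from that table.
- Under 8.6.1 the explanation has to be discussed with the Medical Monitor, and 8.5.1 calls for a work-up and repeat testing two to three times weekly. A carrier state known at entry, with liver tests within the entry limit, does not by itself account for a new rise.

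**Conclusion.** The point holds as an eligibility defect of limited size. Exclusion 7 uses the wrong nucleic acid for one of its three viruses. Taken with Appendix B, it gives a surface-antigen-positive subject a discretionary route to entry on a result that is not informative for that virus. Most likely no subject in a trial of this size is affected, even on the ceiling assumptions. The percent change in plasma AGT, its analysis, the sample size and the ALT/AST tabulation are all untouched.

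The conclusion rests on the written wording and on the two general facts about hepatitis B stated above. It does not depend on the assumed prevalence. The documents do not show that carriers would in practice be admitted, only that the written rule does not settle the question properly.

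**What to change.** Make the same change in Protocol 5.2 item 7 and in the synopsis:

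1. Name the confirmatory test by virus: RNA for HIV and hepatitis C, DNA for hepatitis B.
2. Reconcile item 7 with Appendix B by stating explicitly whether a surface-antigen-positive subject is excluded or may be considered under the Medical Monitor consultation. Either choice should be worded so that no such subject is cleared by an RNA result or left outside both sentences. Which choice to make is for the sponsor.

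The cost is a sentence or two in two places. Confirmatory testing is already part of the criterion, so no visit is added. The downside is that an occasional surface-antigen-positive subject may not be enrolled.

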## 6. STUDY PROCEDURES

### 6.1. Study Schedule

All required study procedures are outlined in [Appendix A](#), [Appendix B](#) and [Appendix C](#).

The length of each subject's participation in the study is approximately 6 months that includes a 4-week Screening Period, 8-week Treatment Period, and a 13-week Post-Treatment Evaluation Period.

All BP assessments will be conducted according to Section [6.1.1.1](#) (Seated BP Measuring Instructions at Each Visit) and Section [6.1.1.2](#) (Orthostatic BP Assessment).

The safety of ISIS 757456 will be continually monitored throughout the trial by the Investigator and the Sponsor Medical Monitor.

#### 6.1.1. Screening

Written informed consent for the study will be obtained prior to the performance of any study-related procedures including screening procedures. A 4-week period is provided for completing screening assessments and determining subject eligibility for the study. Safety labs may be re-tested up to 2 additional times for determination of subject eligibility after consultation with the Sponsor Medical Monitor. AGT may be re-tested up to 1 additional time for determination of subject eligibility after consultation with the Sponsor Medical Monitor.

During the Screening Period, subjects will undergo a medical history (including cardiovascular disease risk factors) and physical examination including vital signs, orthostatic hypotension assessment, 12-lead ECG, and have blood and urine samples taken for clinical laboratory testing. Subjects will be screened for HIV, HepB, and HCV.

During the Screening Period the study site will also education subjects regarding a low sodium diet.

The study site will record basic personal details about you, including your name, contact details, gender, height, weight, date of birth, age, ethnicity, and racial origin (to be used only for clinical purposes), as well as information on your medical history, and clinical data collected about your participation in the study.

#### 6.1.1.1. Seated Blood Pressure Measuring Instructions at Each Visit

##### Subject Instructions

- Subject should have abstained from smoking, exercise and caffeine use at least 30 minutes prior to BP measurements
- Subject should be wearing a loose, short-sleeved top. If subject is wearing a long-sleeved or tight garment around the arm, provide a gown or remove the arm from the sleeve
- Subject should be comfortably seated (e.g., with his/her back against the chair, feet flat on the floor)

- Subject's arm should be bent at the elbow and supported by a table

### Observer Instructions

- Confirm with that the subject has abstained from smoking, exercise and caffeine use at least 30 minutes prior to measurement
- Place the cuff on the subject's upper arm at the level of the heart and centered at the midpoint of the humerus
- Leave subject alone for 5 minutes in a quiet setting
- After 5 minutes, return and take 3 readings, with 60 seconds between readings
- Document the average of the 3 readings

### BP Results

At the screening visit, measure the BP per instructions above with both the right and left arm. The arm with the highest BP (that meets inclusion/exclusion criteria) will be used at each subsequent visit.

#### 6.1.1.2. Orthostatic Blood Pressure Assessment

An orthostatic BP assessment will be done at Screening. BP and pulse rate will be assessed 2 times (Table 2). The subject will lie down (supine) for at least 5 minutes, then BP and pulse rate will be measured. The subject will then change to a standing position and the BP and pulse rate measurements will be repeated after standing greater than 1 minute, but less than or equal to 3 minutes.

Borderline orthostatic hypotension will be defined as a confirmed (sequence must be repeated to confirm) decrease in SBP  $\geq 17$  mmHg and/or a decrease in DBP of  $\geq 7$  mmHg from BP at supine position. During the study, orthostatic hypotension will be defined as a confirmed (sequence must be repeated to confirm) decrease in SBP of  $\geq 20$  mmHg and/or a decrease in DBP of  $\geq 10$  mmHg after standing greater than 1 minute, but less than or equal to 3 minutes. The diagnosis will be made specific to each visit with no comparison to Baseline (Study Day 1 pre-dose) values.

**Table 2: Orthostatic Hypotension Assessment**

Position	Time in Position	Vital Signs Assessed
Supine	5 minutes	BP and pulse rate after 5 minutes
Standing	> 1 to $\leq 3$ minutes	BP and pulse rate assessed within > 1 to $\leq 3$ minutes of standing

#### 6.1.2. Treatment Period

Eligible subjects will be administered Study Drug (ISIS 757456 or placebo) on a weekly basis (8 weeks) as well as an additional dose on Study Day 3 for a total of 9 doses. Review of the in-clinic BP should be performed prior to administering the Study Drug.

Safety and clinical laboratory evaluations as well as blood sampling for PK analysis will be performed periodically throughout the Treatment Period ([Appendix A](#), [Appendix B](#) and [Appendix C](#)). Any AEs and concomitant medications will be recorded. All safety data including AEs, BP, and concomitant medications will be reviewed by the Sponsor's Medical Monitor or designee on an ongoing basis throughout the trial.

The subject is expected to maintain a low sodium diet throughout the study. The study site will counsel and ask the subject at each in-clinic visit if (s)he is maintaining a low sodium diet.

Subjects who discontinue the Treatment Period early will continue in the study following the post-treatment evaluations (Section [6.1.3](#)).

